### **5.3. Control Treatment**

Not applicable.

### **5.4. Dose Interruptions and Reductions**

All confirmed or suspected severe acute respiratory syndrome coronavirus 2 (SARS-CoV-2) infection events must be recorded in the eCRF. Please refer to Section 17.7 for additional information on dose modification.

#### **5.4.1. Dose Interruptions**

The Investigator will evaluate which toxicities are attributed to the study drug and adjust the dose of the drug as recommended below. All dose modifications should be based on the worst preceding toxicity (NCI-CTCAE version 4.03). Specific criteria for interruption, re-initiation, dose reduction and/or discontinuation of DS-8201a are listed in Table 5.2. For Grade 3 or Grade 4 events, monitoring (including local lab tests when appropriate) should be performed at intervals no greater than 7 days until the AE is determined to be resolving or discontinuation of study treatment is decided.

Prophylactic or supportive treatment for expected toxicities, including management of study-drug induced AEs will be as per the treating physician's discretion and institutional guidelines.

In addition, Investigators may consider dose reductions or discontinuations of the study drug according to the subject's condition and after discussion with the Daiichi Sankyo's Medical Monitor or designee.

#### 5.4.2. Dose Reductions

Note: There will be no dose modifications for Grade 1 or Grade 2 AEs unless specified in [Table 5.2](#) and Section 3.2.5.

Two dose reductions are permitted in this study. The adjustment for reduced dosing of DS-8201a will be as shown in [Table 5.1](#).

**Table 5.1 Reference Scheme of Dose Reduction**

Dose level before dose interruption		Dose level after first dose reduction		Dose level after second dose reduction
6.4 mg/kg	→	5.4 mg/kg	→	4.4 mg/kg

The Investigator may consider dose reductions or discontinuation of the study drug according to the condition of the subject and after discussion with the Sponsor.

Once the dose of DS-8201a has been reduced because of toxicity, all subsequent cycles should be administered at that lower dose level unless further dose reduction is required. More than 2 dose reductions are not allowed and the subject will be withdrawn from the study treatment if further toxicity meeting the requirement for dose reduction occurs.

#### Dose Interruption and Modification/Toxicity Management Guidelines:

A dose can be delayed for up to 28 days from the planned date of administration, or 49 days from the previously administered dose. If a subject is assessed as requiring a dose delay of longer than 28 days from the planned date of administration, the subject will be withdrawn from the study.

Treatment cycles for a subject for whom DS-8201a dosing is temporarily withheld for any reason may have future cycles scheduled based on the date of the last DS-8201a dose.

All confirmed or suspected COVID-19 infection events must be recorded in the eCRF. Please refer to Section 17.7 for additional information on dose modification. The dose modification schedule is presented in [Table 5.2](#).

**Table 5.2 Dose or Schedule Modification for DS-8201a**

Worst toxicity NCI-CTCAE version 4.03 Grade (unless otherwise specified)	Management Guidelines for DS-8201a
No toxicity	Maintain dose and schedule
Infusion-Related Reaction	
See Section 3.2.5.1 for management of infusion-related reactions	
Hematologic Toxicity	
Neutrophil Count Decreased	
Grade 3 (<math>1.0 \times 10^9/L</math> to <math>0.5 \times 10^9/L</math>)	Delay dose until resolved to $\leq$ Grade 2, then maintain dose
Grade 4 (<math><0.5 \times 10^9/L</math>)	Delay dose until resolved to $\leq$ Grade 2, Reduce dose by 1 level
Febrile neutropenia (ANC <math><1 \times 10^9/L</math>, fever >38.3°C or a sustained temperature of $\geq 38^\circ\text{C}$ for more than 1 hour)	Delay dose until resolved, Reduce dose by 1 level
Lymphocyte Count Decreaseda	
Grade 1 to Grade 3 lymphopenia	No dose modification
Grade 4 (<math><0.2 \times 10^9/L</math>)	Delay dose until resolved to $\leq$ Grade 2: 
 
• If resolved in <math>\leq 14</math> days from day of onset, maintain dose
 
• If resolved in >14 days from day of onset, reduce dose 1 level
 

Anaemia	
Grade 3 (Hb <math><8.0</math> g/dL); transfusion indicated	Delay dose until resolved to $\leq$ Grade 2, then maintain dose
Grade 4 Life threatening consequences; urgent intervention indicated	Delay dose until resolved to $\leq$ Grade 2, then reduce dose 1 level
Platelet Count Decreased	
Grade 3 (platelets <math><50 \times 10^9/L</math> to <math>25 \times 10^9/L</math>)	Delay dose until resolved to $\leq$ Grade 1: 
 
• If resolved in <math>\leq 7</math> days from day of onset, maintain dose
 
• If resolved in >7 days from day of onset, reduce dose 1 level
 

Grade 4 (platelets <math><25 \times 10^9/L</math>)	Delay dose until resolved to $\leq$ Grade 1, then reduce dose 1 level
Cardiac Toxicity	
See Section 3.2.5.1 for management of cardiac toxicities	
Ocular	
Grade 3	Delay dose until resolved to $\leq$ Grade 1: 
 
• If resolved in <math>\leq 7</math> days from day of onset, maintain dose
 
• If resolved in >7 days from day of onset, reduce dose 1 level
 

Grade 4	Discontinue subject from study treatment
Pulmonary Toxicity	
Please see Section 3.2.5.2 for management of pulmonary toxicity	
Blood creatinine increased	
Grade 3 (>3.0 to <math>6.0 \times \text{ULN}</math>)	Delay dose until resolved to $\leq$ Grade 2 or Baseline, then reduce dose 1 level
Grade 4 (>6.0 $\times$ ULN)	Discontinue subject from study treatment

Hepatic Toxicity	
Aspartate Aminotransferase (AST) or Alanine Aminotransferase (ALT) with Simultaneous total Bilirubin (TBL)	
AST/ALT $\geq 3.0 \times$ ULN with simultaneous TBL $> 2.0 \times$ ULN	
Delay study medication until drug-induced liver injury can be ruled out.
 
If drug-induced liver injury is ruled out, the subject should be treated accordingly, and resumption of study drug may occur after discussion between the Investigator and the Sponsor.
 
If drug-induced liver injury cannot be ruled out from diagnostic workup, permanently discontinue study treatment.
 
Monitor AST/ALT and TBL twice weekly until resolution or return to baseline.

Aspartate Aminotransferase (AST) or alanine Aminotransferase (ALT)	
Grade 2 ( $>3.0$ to $5.0 \times$ ULN )	No action for Grade 2 AST/ALT
Grade 3 : $>5.0$ to $20.0 \times$ ULN. In subjects without liver metastases and subjects with liver metastases and baseline level $\leq 3 \times$ ULN	
Repeat testing within 3 days. Delay dose until resolved to <math>\leq</math> Grade 1 if baseline <math>\leq 3 \times</math> ULN, otherwise delay dose until resolved to <math>\leq</math> baseline, then:
 
 
• If resolved in <math>\leq 7</math> days from day of onset, maintain dose
 
• If resolved in <math>>7</math> days from day of onset, reduce dose 1 level
 

Grade 3: $>8.0$ to $20.0 \times$ ULN) In subjects with liver metastases, if the baseline level was $>3 \times$ ULN	
Repeat testing within 3 days. Delay dose until resolved to <math>\leq</math> baseline level, then:
 
 
• If resolved in <math>\leq 7</math> days from day of onset, maintain dose
 
• If resolved in <math>>7</math> days from day of onset, reduce dose 1 level
 

Grade 4 ( $>20 \times$ ULN )	Discontinue subject from study treatment
Total Bilirubin (TBL)	
Grade 2 ( $>1.5$ to $3.0 \times$ ULN )	
If no documented Gilbert's syndrome or liver metastases at baseline, delay dose until resolved to <math>\leq</math> Grade 1:
 
 
• If resolved in <math>\leq 7</math> days from day of onset, maintain dose
 
• If resolved in <math>>7</math> days from day of onset, reduce dose 1 level
 
 
If documented Gilbert's syndrome or liver metastases at baseline, continue study treatment

Grade 3 ( $>3.0$ to $10.0 \times$ ULN )	
If no documented Gilbert's syndrome or liver metastases at baseline, repeat testing within 3 days. Delay dose until resolved to <math>\leq</math> Grade 1:
 
 
• If resolved in <math>\leq 7</math> days from day of onset, reduce dose 1 level
 
• If resolved in <math>>7</math> days from day of onset, discontinue DS-8201a
 
 
If documented Gilbert's syndrome or liver metastases at baseline, repeat testing within 3 days. Delay dose until resolved to <math>\leq</math> Grade 2:
 
 
• If resolved in <math>\leq 7</math> days from day of onset, reduce dose 1 level
 
• If resolved in <math>> 7</math> days from day of onset, discontinue DS-8201a
 

Grade 4 ( $>10.0 \times$ ULN)	Discontinue subject from study treatment
Blood Alkaline Phosphatase (ALP) Increased	
Grade 3 or 4 ( $>5.0 \times$ ULN)	No modification unless determined by the Investigator to be clinically significant or life-threatening.
Gastrointestinal	
Nausea	
Grade 3	
Delay dose until resolved to <math>\leq</math> Grade 1
 
 
• If resolved in <math>\leq 7</math> days from day of onset, maintain dose
 
• If resolved in <math>>7</math> days from day of onset, reduce dose 1 level
 

Diarrhea/Colitis	
Grade 3	Delay dose until resolved to $\leq$ Grade 1

	
 
• If resolved in <math>\leq 3</math> days from day of onset, maintain dose
 
• If resolved in <math>> 3</math> days from day of onset, reduce dose 1 level
 

Grade 4	Discontinue subject from study treatment
Other Laboratory Adverse Events	

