### 4.1. Inclusion Criteria

Subjects must satisfy all of the following criteria to be included in the study:

1. Chinese patients aged  $\geq 20$  years
2. Pathologically documented HER2-positive advanced/unresectable or metastatic gastric, GEJ adenocarcinoma, or breast cancer, with both:
  - a. HER2-positive disease documented as: immunohistochemistry (IHC) 3+ positive, and/or fluorescence in situ hybridization (ISH)  $\geq 2.0$  that is refractory to or intolerable with standard treatment, or for which no standard treatment is available. For subject with gastric or GEJ adenocarcinoma cancers, it is preferable to determine HER2 status after completing the last HER2-targeting treatment.
  - b. Documented disease progression (by the Investigator's assessment) after at least one regimen of trastuzumab therapy in metastatic or unresectable locally advanced/recurrent setting.
3. ECOG PS 0 to 1.
4. LVEF  $\geq 50\%$  by either ECHO or MUGA scan within 28 days before registration.
5. Adequate organ function within 7 days before registration defined as:

Item	Laboratory value
Platelet count	$\geq 100,000/\text{mm}^3$ (platelet transfusion is not allowed within 1 week prior to screening assessment)
Hemoglobin (Hb)	$\geq 9$ g/dL (red blood cell transfusion is not allowed within 1 week prior to screening assessment)
Absolute neutrophil count (ANC)	$\geq 1500/\text{mm}^3$ (granulocyte colony-stimulating factor administration is not allowed within 1 week prior to screening assessment)
Creatinine	$\leq 1.5 \times$ upper limit of normal (ULN), or creatinine clearance $\geq 60$ mL/min as calculated using the Cockcroft-Gault equation
Aspartate aminotransferase (AST)/alanine aminotransferase (ALT)	$\leq 3 \times$ ULN (if liver metastases are present, $\leq 5 \times$ ULN)

Total bilirubin (TBL)	$\leq 1.5 \times \text{ULN}$ or $< 3 \times \text{ULN}$ in the presence of documented Gilbert's Syndrome or liver metastases at baseline
Prothrombin time and activated partial thromboplastin time	$\leq 1.5 \times \text{ULN}$

6. Adequate treatment washout period before registration, defined as:

Treatment	Washout period
Major surgery	$\geq 4$ weeks
Radiation therapy	$\geq 4$ weeks (if palliative stereotactic radiation therapy excludes abdomen, $\geq 2$ weeks)
Autologous transplantation	$\geq 3$ months
Hormonal therapy	$\geq 2$ weeks

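### Table 5.2 does not say whether the combined AST/ALT–bilirubin hold overrides the Grade 2 bilirubin instruction to keep dosing in subjects with liver metastases or Gilbert's syndrome (minor safety inconsistency)

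*Combined protocol and SAP*

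**What the plan says.** Table 5.2 of the protocol treats hepatic toxicity under separate headings.

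- **AST/ALT with simultaneous TBL.** Trigger: AST/ALT at or above 3.0x ULN and TBL above 2.0x ULN at the same time, with no exemption for any subgroup. Order: "Delay study medication until drug-induced liver injury can be ruled out". If injury is ruled out, "resumption of study drug may occur after discussion between the Investigator and the Sponsor". Otherwise: "If drug-induced liver injury cannot be ruled out from diagnostic workup, permanently discontinue study treatment".
- **AST/ALT alone.** Grade 2 (above 3.0 to 5.0x) calls for no action. The Grade 3 delay starts above 5.0x ULN, or above 8.0x in subjects with liver metastases whose baseline exceeded 3x.
- **TBL alone.** Grade 2 (above 1.5 to 3.0x) calls for a delay, with an exception: "If documented Gilbert's syndrome or liver metastases at baseline, continue study treatment". Grade 3 (above 3.0 to 10.0x) calls for a delay in all subjects.

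Three general statements bear on which row applies. Section 5.4.1 says "All dose modifications should be based on the worst preceding toxicity". Section 5.4.2 says "There will be no dose modifications for Grade 1 or Grade 2 AEs unless specified in" Table 5.2 and Section 3.2.5. The left-hand column of the table is headed "Worst toxicity NCI-CTCAE version 4.03 Grade (unless otherwise specified").

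**The concern.** The TBL Grade 2 exception names a subgroup and gives it a positive instruction to keep dosing, whatever the transaminases are doing. The combined row names a laboratory pattern and orders a hold, whatever the subgroup. Where the two meet, a site has two written instructions and no rule for choosing between them.

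The pattern matters because Section 8.5 uses the same cut-offs to define potential Hy's Law cases, and safety and tolerability are the primary objective. Take a subject with Gilbert's syndrome whose TBL stays at 2.5x ULN while AST rises from 1x to 4x ULN. A site following the exception would go on dosing, and Table 5.2 would then require neither a hold nor a work-up for drug-induced liver injury (DILI).

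**Working it through.** The plan gives no figure to reproduce. The check intersects the row triggers and then looks for a ranking rule.

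**Step 1: the overlap in TBL.** Combined row: TBL > 2.0x. TBL Grade 2: > 1.5 to 3.0x. Intersection: > 2.0 to 3.0x, together with AST/ALT ≥ 3.0x. At or below 2.0x the combined row is not met. Above 3.0x the TBL row also delays or discontinues. Without liver metastases or Gilbert's syndrome the TBL Grade 2 row itself delays. The collision is therefore confined to this band in these two subgroups.

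**Step 2: where the combined row is the only hold.** Within the band, the AST/ALT rows order no hold until Grade 3.

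- Gilbert's syndrome alone, or metastases with baseline AST/ALT ≤ 3x: the AST/ALT delay starts above 5.0x, so the combined row is the only hold from 3.0 to 5.0x.
- Metastases with baseline AST/ALT > 3x: the delay starts above 8.0x, so it is the only hold from 3.0 to 8.0x. From above 5.0x to 8.0x no AST/ALT row gives this subgroup any instruction.

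**Step 3: illustrative cases (multiples of ULN).**

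| Subject | AST | TBL | Combined row | AST/ALT row | TBL row |
|---|---|---|---|---|---|
| Gilbert's | 1 | 2.5 | not met | none | continue |
| Gilbert's | 4 | 1.8 | not met | no action | continue |
| Gilbert's | 4 | 2.5 | **delay** | no action | **continue** |
| Gilbert's | 4 | 3.2 | delay | no action | delay |
| Metastases, baseline AST 4 | 6 | 2.5 | **delay** | none (hold above 8) | **continue** |
| Metastases, baseline AST 2 | 6 | 2.5 | delay | delay | continue |
| Neither | 4 | 2.5 | delay | no action | delay |

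In the two bold rows, whether the subject is held depends entirely on which instruction the site follows.

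**Step 4: can it arise?** Section 4.1, item 5, allows AST/ALT up to 5x ULN "if liver metastases are present" and TBL below 3x ULN with liver metastases or Gilbert's syndrome. A subject with metastases can enrol already inside the overlap. A subject with Gilbert's syndrome alone must enter with AST/ALT at or below 3x, so except at exactly 3.0x the overlap can only arise on study.

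**Step 5: does any text rank the rows?**

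- The worst-preceding-toxicity rule in Section 5.4.1 orders CTCAE grades. In the core case (AST 4x, TBL 2.5x) both analytes are Grade 2, and the combined row has no grade.
- The Section 5.4.2 note defers to Table 5.2, which contains both instructions.
- The qualifier in the column header concerns grading. It makes room for an ungraded row but does not rank it.
- Investigator discretion (Section 5.4.1 and the foot of Table 5.2) covers reductions and discontinuations and sets no order between rows.

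None of these settles the question.

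**The case against.** The strongest reply is that the layout already gives the answer. Each row states what one toxicity requires, and the combined pattern has its own heading, separate from the AST/ALT and TBL headings. On that reading, the exception means only that Grade 2 bilirubin by itself is no reason to hold in this subgroup, and it cannot cancel a hold that another row requires. Other permissive rows work this way: nobody would let the no-modification rule for Grade 1 to 3 lymphopenia cancel a delay for Grade 4 neutropenia. The no-action row for Grade 2 AST/ALT overlaps the combined row in every subject, and it yields naturally without a stated rule. The combined row is also both the stricter and the more specific in laboratory terms.

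Most of this stands. The hold is the more natural reading, and a careful investigator would probably delay. What remains is that the exception is a positive order to a named subgroup, is not restricted to isolated bilirubin rises, and is ranked nowhere.

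A second reply is that Section 8.5 requires potential Hy's Law events to be reported within 24 hours, with no exemption for these subgroups and with a targeted questionnaire. This is a real but partial backstop. It brings the case to the sponsor's attention, but it does not order a hold.

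A reader might infer that the protocol directs sites to dose through potential Hy's Law events. The documents do not support that, because the combined row orders the opposite and has no exemption.

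**Conclusion.** The inconsistency holds, and it is minor. It is confined to subjects with liver metastases or documented Gilbert's syndrome at baseline who have AST/ALT at or above 3.0x ULN with simultaneous TBL above 2.0 to 3.0x ULN. Following the exception would leave no hepatic row ordering a hold at AST/ALT 3 to 5x ULN, or up to 8x ULN with liver metastases and baseline AST/ALT above 3x.

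The documents do not say how many of the approximately 12 subjects will have liver metastases or Gilbert's syndrome, or will reach these values. The number affected is unknown and may be zero. The conclusion rests on the wording of the rows and on the absence of a ranking rule in the dosing text, and not on any assumed event rate.

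A reader might also infer that the safety analyses are compromised. They are not. Sections 11.4.3.1 and 11.4.3.2 define treatment-emergent events and laboratory shifts by onset, worsening and grade relative to baseline, and neither definition depends on which row a site follows. No sample-size figure, analysis set or planned summary changes.

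**What to change.** Either of two edits to Table 5.2 is enough:

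1. Limit the TBL Grade 2 continue instruction to subjects who do not meet the combined row, that is, AST/ALT below 3x ULN or TBL at or below 2x ULN.
2. Add one sentence stating that the combined AST/ALT–TBL row takes precedence over the single-analyte rows.

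The second also settles the overlap with the no-action row for Grade 2 AST/ALT. Neither edit touches eligibility, endpoints, sample size or the 24-hour report in Section 8.5. No baseline-relative trigger or new exclusion criterion is needed to remove the conflict. Nor is an extra baseline flag: it would not resolve the conflict, and screening laboratory values are already collected (Section 6.1).

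The cost is one clause or sentence in an amendment, plus a small clinical downside. Some subjects with metastases whose raised values have not changed since entry may be held briefly until DILI is ruled out and resumption is agreed with the Sponsor. The combined row already provides that route back to treatment.

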Grade 3 (Levels consistent with myocardial infarction as defined by the manufacturer)	
Perform ECG in triplicate.
 
Repeat troponin testing at 6 hours (<math>\pm 1</math> hour) and 12 hours (<math>\pm 1</math> hour) after initial troponin test.
 
Follow institutional guidelines for management of detectable troponin testing. If AMI confirmed, discontinue subject from study therapy.
 
Otherwise, delay dose until resolved to <math>\leq</math> Grade 1:
 
 
• If resolved in <math>\leq 7</math> days from day of onset, maintain dose.
 
• If resolved in <math>> 7</math> days from day of onset, reduce dose 1 level.
 

ALT = alanine aminotransferase, AST = aspartate aminotransferase, NCI-CTCAE = National Cancer Institute Common Terminology Criteria for Adverse Events, ECG = electrocardiogram, Hb = hemoglobin, TBL = total bilirubin, ULN = upper limit of normal

a. There will be no dose modifications for Grade 1 to Grade 3 lymphopenia. All dose modifications should be based on the worst preceding toxicity.

In addition, investigators may consider dose reductions or discontinuations of the study drug according to the subject's condition and after discussion with the Daiichi Sankyo's Medical Monitor or designee.

## **5.5. Method of Assessing Treatment Compliance**

All doses of the study drug will be administered by the Investigator or other designated study personnel. Therefore, treatment compliance will be guaranteed as long as the subject attends each visit for the administration of study drug. Start and stop date/time of injection, amount of drug administered, and reason for change or interruption (if applicable) must be recorded in medical record by clinical study personnel. These data will be recorded in the electronic case report form (eCRF).

## **5.6. Prior and Concomitant Medications**

Medications used from the time the subject signs the ICF to Follow-up (F/U) (+7 days) will be recorded. All concomitant medications will be recorded in the eCRF.

### **5.6.1. Prohibited Concomitant Medications/Activities**

With the exception of medications that are under investigation in the study (e.g. standard of care, comparators, or combination therapies), the following medications and products are prohibited during this study. The Sponsor must be notified if a patient receives any of these during the study.

- Other anticancer therapy, including cytotoxics, targeted agents, immunotherapy, antibody, retinoid or hormonal therapy. Concurrent use of hormones for no cancer-related conditions (e.g. insulin for diabetes and hormone replacement therapy) is acceptable.
- Other investigational agents.
- Radiotherapy (except for palliative radiation to known metastatic sites as long as it does not affect assessment of response or interrupt treatment for more than the maximum time specified in dose modification section).
- Radiotherapy to the thorax.
- Concomitant use of chronic systemic (IV or oral) corticosteroids or other immunosuppressive medications except for managing AEs; (inhaled steroids and intra-articular steroid injections are permitted in this study).

Subjects with bronchopulmonary disorders who require intermittent use of bronchodilators (such as albuterol) will not be excluded from this study.

- Concomitant treatment with chloroquine or hydroxychloroquine is not allowed during the study treatment. Refer to Section 17.7 for further details.

#### Permitted Therapies/Products

1. Hematopoietic growth factors may be used for prophylaxis or treatment based on the clinical judgment of the Investigator.

2. Concomitant use of dietary supplements, medications not prescribed by the Investigator, and alternative/complementary treatments is discouraged, but not prohibited.
3. Prophylactic or supportive treatment of study-drug induced AEs will be otherwise as per Investigator's discretion and institutional guidelines.
4. Based on the currently available clinical safety data, it is recommended that patients receive prophylactic anti-emetic agents prior to infusion of T-DXd and on subsequent days. Antiemetics such as 5-hydroxytryptamine receptor (5-HT3) antagonists or Neurokinin-1 (NK1) receptor antagonists and/or steroids (e.g. dexamethasone) should be considered and administered in accordance with the prescribing information or institutional guidelines.

